10.4.4 SAFETY ANALYSES

Safety endpoints include clinical measures intended to evaluate the direct effect of the device at the site of placement. To evaluate the effect of the ETT at the local level we will be assessing subjective and objective measures of laryngeal anatomy and function, in addition to any device related adverse events. We will record: 1) airway complications at the time of ETT insertion; 2) stridor immediately after extubation; 3) requirement for stridor treatment (racemic epinephrine, helium-oxygen gas mixture); or 4) reintubation within 24 hours due to upper airway complications such as stridor or obstruction. Long-term safety will be assessed by ascertaining the persistence of airway sequelae six months after randomization using a standardized questionnaire via in-person interview. At the in-person interview, participants will be administered a structured interview to collect information for residual complaints involving the upper airway and any airway problems requiring the consultation of a specialist (Appendix II). Data collected include the presence of persistent throat discomfort or pain, residual hoarseness, change in voice, and dyspnea. If a visit to a specialist for evaluation and/or treatment of speech, swallowing, or breathing problems occurred, the medical record will be reviewed. If moderate to severe airway symptoms are identified, one the PIs will evaluate the airway and will refer the patient to the primary care provider or to a specialist, as appropriate.

Adverse Events: As defined in 21 CFR 312.32. Tabulation or summary of AEs will be reported at each DSMB meeting and annually to IRB.

10.4.5 BASELINE DESCRIPTIVE STATISTICS

For the baseline descriptive statistics, we will present overall sample summary characteristics, e.g., mean, standard deviations, and percentages. We will also provide summaries of the baseline characteristics stratified by treatment assignment to describe the patient population and to evaluate the balance in the randomization assignment. We will also provide information on data completeness and retention to follow up.

10.4.6 PLANNED INTERIM ANALYSIS

The test of hypothesis for the primary endpoint is a two-sample difference in risk in a group sequential design with one planned interim analysis. The analysis will be conducted when approximately 50 percent of the total sample has been collected. The test of hypothesis for the primary endpoint is a two-

sample difference in risk in a group sequential design with one planned interim analysis according to the design specified in Section 10.4.2.

10.4.7 SUB-GROUP ANALYSES

We will investigate whether the proportion of IVAC and VAEs differs between EVAC-PU-ETT and PVC-ETT among the subgroups of critically ill patients defined by gender and race. Formal comparisons between the treatment groups and patient subgroups will be investigated by fitting logistic regression models with robust variance estimates. We will perform omnibus tests of appropriately specified interaction terms between treatment assignment and patient subgroups.

Also, we will use regression analysis to determine if there are greater/lesser benefits/risks in patient subgroups in the economic analysis.

11 SUPPORTING DOCUMENTATION AND OPERATIONAL CONSIDERATIONS

11.1 REGULATORY, ETHICAL, AND STUDY OVERSIGHT CONSIDERATIONS

11.1.1 INFORMED CONSENT PROCESS

11.1.1.1 CONSENT/ASSENT AND OTHER INFORMATIONAL DOCUMENTS PROVIDED TO PARTICIPANTS

Consent forms describing in detail the study intervention, study procedures, and risks are given to the participant. Due to the emergent situation leading to study enrollment, most participants will be incapacitated at the start of the study intervention. Written documentation of informed consent will be obtained at the earliest feasible opportunity after starting the intervention, either by the participant after regaining decisional capacity, or by the LAR once identified. A copy of the signed consent form will be given to the participant or LAR after written consent has been obtained.

11.1.1.2 CONSENT PROCEDURES AND DOCUMENTATION

This study involves emergency situations with an extremely narrow therapeutic window, minimal risk of harm to subjects, and involves no procedures for which written consent is generally required outside of the research context, it qualifies for the “exception from informed consent required for emergency research” outlined in FDA regulation 21CFR50.24.

The need for emergency endotracheal intubation is a clinical decision that is based on the patient’s condition and the likelihood of significant morbidity or mortality without intervention. In this situation, the therapeutic window for interventional care may be seconds to minutes. In the vast majority of cases,

this therapeutic window represents insufficient time to contact a LAR for consent. In addition, any delay in these emergency situations could be detrimental to the patient. All aspects of clinical care that follow the placement of the device will occur according to usual care. We will make every effort to contact a legal representative during the therapeutic window to ask for consent prior to intubation with a study tube rather than proceeding without consent. However, the need to obtain consent will not impede the clinical need to intubate a patient as the provider sees fit. Emergency intubation will not be delayed as a result of waiting to obtain LAR consent for this study.

It is unlikely that an individual subject may be conscious and able to make health care related decisions. In the event that a patient meets the entry criteria and is awake and alert, the patient is still under considerable duress due to the acute injury. In this situation, an opt-out script informing the patient that he/she is being enrolled in a research study and their right to immediate refusal along with a brief description of the study will be read to the subject by any of the following: trained providers performing the procedure, the ICU nurse, or the respiratory therapist in the ICU. For patients “opting-out,” a non-study tube from standard supply will be used for intubation.

Prior to randomization, there may be other evidence that an individual does not wish to participate in a study. For instance, a LAR or family member is able to communicate a subject’s unwillingness to participate in research studies or there is evidence in the individual’s electronic health record. If we learn that a family or patient is opposed to participating in the research prior to randomizing the patient, then we will not be randomized into this study and the subject will receive a non-study ETT.

If the subject or the LAR is not immediately available to provide consent during the therapeutic window, the research coordinator will attempt to contact the subject’s LAR through hospital discharge as described below.

After the therapeutic window, the research coordinator will attempt to contact the subject’s LAR through hospital discharge. A summary of these efforts will be documented in the study attempted consent logs. The study team will attempt to obtain informed consent for continued participation in the study upon identification of the subjects via the daily intubation and ventilation reports, as well as communication from the team performing the intubation procedure. If the study participant is legally competent but is physically unable to talk or write, an unbiased witness who is neither a study team member nor a family member of the participant can sign the witnessed line on the consent form to enter the patient into the trial. The unbiased witness must observe the consent process.

For the majority of enrolled subjects, it is assumed that patients themselves will be unable to give informed consent due to critical illness, tracheal intubation, and administration of sedative and analgesic drugs, all of which may cloud consciousness, impair communication and decisional capacity. When it is appropriate to obtain informed consent, the patient’s clinical team will be asked for

permission to approach the patient's LAR in person to consent for continued participation in the study at the earliest feasible opportunity.

When it is appropriate, a member of the study team will meet with the LAR to explain why the subject was included in the study without his/her informed consent. The study team will provide the details about the research study and will ask for continued participation in this study. The study team will obtain informed consent. Consent forms will be Institutional Review Board (IRB)-approved and include HIPAA Authorization. The study team will also obtain a signed clinical medical records release form to allow review of the patient's outside medical record when consultation of a specialist is required. The LAR will be asked to read and review the documents. The study team will explain the research study to the LAR and answer any questions that may arise. A verbal explanation will be provided in terms suited to the LAR's comprehension of the purposes, procedures, and potential risks of the study and of the rights of the research participant. During the consent process, the details of the study will be reviewed along with potential risks and benefits, the endpoints of interest, and the process by which these endpoints are evaluated. The LAR will have the opportunity to carefully review the written consent form and ask questions prior to signing. The LAR must be informed that participation is voluntary and that the participant may withdraw from the study at any time, without prejudice. A copy of the informed consent document will be given to the LAR and the participant for their records. The informed consent process will be conducted and documented in the source document. The rights and welfare of the participant will be protected by emphasizing to the LAR that the quality of the participant's medical care will not be adversely affected if they decline to participate in this study.

When face-to-face communication with the LAR is not possible (for instance due to individual being out of town), then the study team will make contact by phone and send information with the consent form by registered mail, email, or by fax with "read receipts" in order to provide this information in a timely fashion and to obtain signatures for the consent form.

If the LAR is told about the research study and the subject's condition improves, the subject will also be informed about the research as soon as is feasible. The LAR, or subject will be given the opportunity to object to the study and refuse participation or withdraw from the study at any time without penalty or loss of benefits to which the subject is otherwise entitled. If the subject or LAR chooses to withdraw from the study after randomization, the study team will discontinue data collection on the patient at that time but will retain the data collected up until the time of withdrawal.

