9 STUDY ASSESSMENTS AND PROCEDURES

9.1 EFFICACY ASSESSMENTS

The initial study intervention (randomization and placement of a study device [tracheal intubation]) will be performed under exception from informed consent since the event will occur in an emergency situation. At the first available opportunity, an attempt will be made to obtain written informed consent from the participant or the authorized representative to continue participation in the study. Subjects

who have been randomized will be identified within 24 hours of intervention (tracheal intubation), and an attempt to approach the patient or more likely their legally authorized representative will be made immediately upon identification. In some cases, it may be difficult to identify the LAR immediately, but every effort will be made to obtain informed consent within 72 hours of randomization. Throughout the patient's hospitalization, data will be collected continuously from the time of randomization until hospital discharge or death.

A summary of the clinical data variables and definitions are listed below:

Baseline variables

Demographics: Patient demographic characteristics include age in years on the day of hospital admission, gender, race, ethnicity, weight and height, and county/state of residence. Participants' address and contact information will be maintained separately from the case report form and the study datasets, and linked via the study ID number, to enable re-contacting the participants after hospital discharge.

Clinical variables

Intubation procedure: PVC-ETT patients will be treated according to usual care, while EVAC-PU-ETT patients will receive continuous subglottic suctioning until removal of the ETT. As per the manufacturer's recommendation, continuous low-pressure suction at -20 mm Hg will be applied to the suction port. Procedural details of the intubation procedures will be collected as part of standard pre-formed intubation procedure notes. These details include indication for tracheal intubation, ETT type and size, methods of preoxygenation, induction medication, and instruments used. To quantify difficulty with laryngoscopy and ETT insertion, we will record the number of laryngoscopy attempts, and use of gum-elastic bougie to guide insertion of the tube. Furthermore, immediate complications will be gathered including aspiration noted during laryngoscopy, pharyngeal and tracheal injury, and extent of oxygen desaturation.

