VAP bundles and concomitant treatments that affect VAP: 1) Semi-recumbent position by capturing head of bed position (% of time >30° as automatically recorded by electronic beds); 2) stress ulcer prophylaxis, enteral calorie intake; 3) performance of oral hygiene, 4) use of neuromuscular blocking agents; 5) documentation of cuff pressure and application of subglottic suctioning; 6) Daily sedation vacation and spontaneous breathing trial (SBT).

VAP Treatment: Initial antimicrobial therapy is directed by hospital-wide guidelines. Use of respiratory antimicrobials and their duration will be collected.

During the ICU stay we will also collect the daily SOFA. As a summary measure, we will compute the mean of the daily score during the ICU stay.

Hospital stay variables: After discharge from the ICU, patients will be followed to obtain information on safety, disposition and antimicrobial treatment for VAP.

6-month follow-up: All patients will be followed-up six months after randomization with a structured in-person interview to screen for the presence of and assess airway symptoms or persistent sequelae of laryngeal dysfunction (Appendix II).¹⁰⁶ Any need for consultation of a specialist for airway complaints will be recorded and information abstracted from the medical record if appropriate. The clinical medical records release form collected at the time of informed consent will allow access to the subject's outside medical record for data related to the breathing problem. Quality of life will be also assessed, as measured by the physical component summary and the mental component summary of the Medical

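### Active attempts to reach a representative for consent end at hospital discharge, leaving survivors discharged without capacity and with no representative located no stated active route to consent for the 6-month visit

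*Combined protocol and SAP*

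**What the plan says.** - **Consent is for staying in the study.** The study tube is placed under exception from informed consent. Staff then try "to obtain written informed consent from the participant or the authorized representative to continue participation in the study" (section 9.1; sections 7.1.1 and 11.1.1.2 agree). The target is soft: "every effort will be made to obtain informed consent within 72 hours of randomization".
- **The search for a representative has an end point.** Section 11.1.1.2 gives it twice, in consecutive paragraphs. The second reads: "LAR through hospital discharge. A summary of these efforts will be documented in the study attempted consent logs". The section also assumes that most enrolled patients cannot consent for themselves.
- **Consent itself has no end point.** Section 11.1.1.1: "Written documentation of informed consent will be obtained at the earliest feasible opportunity after starting the intervention", and "either by the participant after regaining decisional capacity, or by the LAR once identified".
- **Remote consent is available.** If the representative cannot be met in person, "then the study team will make contact by phone and send information with the consent form by registered mail, email, or by fax" (section 11.1.1.2).
- **Everyone is expected at month 6.** Section 9.1: "All patients will be followed-up six months after randomization with a structured in-person interview". Section 5.1 says the same, and section 10.3 puts every patient intubated from a study kit and admitted to an adult ICU in the ITT population.
- **Missing outcomes.** Section 10.2 rests the primary analysis on missing at random and offers standard multiple imputation as the sensitivity analysis. No attrition figure is given.

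No section says what happens to a patient for whom consent is never obtained. Section 11.1.1.2 stops data collection only when the subject or representative chooses to withdraw.

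**The concern.** The sections fit together for a patient who regains capacity or whose representative is found in hospital. They do not cover a survivor discharged, for example to a care facility, still without capacity and with no representative located. Section 11.1.1.2 has by then ended the active search, while section 9.1 still expects a research interview.

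If such patients go unassessed, the loss is unlikely to be random. Lack of capacity at discharge plausibly goes with cognitive impairment at six months, which is a primary endpoint. Observed prevalence would then be too low, and there would be fewer scored patients for cognition, quality of life and the airway interview. The primary analysis is stated to be valid under missing at random, and standard multiple imputation normally rests on the same assumption, so neither tests this mechanism.

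**Working it through.** **Inputs from section 10.2.** 537 per arm; impairment 0.40 in control; risk difference 0.09 (0.40 vs 0.31); SF-36 difference 0.17 SD; two-sided alpha 0.05; power at least 80%; no allowance for missing data.

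**Step 1: the plan's own figures.**
- Cognition: power = Φ{[0.09 − 1.96·√(2·0.355·0.645/537)] / √[(0.40·0.60 + 0.31·0.69)/537]} = Φ{(0.0900 − 0.0572)/0.0291} ≈ Φ(1.127) = 87.0%.
- SF-36: power = Φ(0.17·√(537/2) − 1.96) = Φ(0.826) = 79.5%.

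Both agree with the plan to within rounding, provided all 1,074 patients are scored.

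**Step 2: loss that depends on impairment.** The documents give no rate of consent never obtained, so every rate below is an assumption. Let a be the share of impaired patients lost and b the share of unimpaired patients lost, the same in both arms. Observed prevalence = π(1−a) / [π(1−a) + (1−π)(1−b)].

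| a, b | Control | EVAC | Difference | Scored | Power |
|---|---|---|---|---|---|
| 0, 0 | 0.400 | 0.310 | 0.090 | 537 / 537 | 87% |
| 0.10, 0.03 | 0.36/0.942 = 0.382 | 0.279/0.9483 = 0.294 | 0.088 | 506 / 509 | 84% |
| 0.15, 0.05 | 0.34/0.910 = 0.374 | 0.2635/0.919 = 0.287 | 0.087 | 489 / 494 | 83% |

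The difference between arms in numbers lost is small: about 31 vs 28 patients in the second row and 48 vs 44 in the third.

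**Step 3: heavier loss, and the direction of bias.** Let a fraction d be lost in each arm, with impairment rate q among the lost. Observed prevalence = (π − d·q)/(1 − d).
- q = 0.6 to 0.8 in lost controls, with the same risk ratio (0.31/0.40) among lost EVAC patients. At d = 0.10, control prevalence is 0.378 to 0.356, the difference 0.085 to 0.080, and power 80% to 76%. At d = 0.20, control prevalence is 0.350 to 0.300, the difference 0.079 to 0.068, and power 70% to 61%.
- The same q in both arms. The difference becomes 0.09/(1 − d), that is 0.100 at d = 0.10 and 0.113 at d = 0.20. It is inflated.

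Prevalence is understated in every case, but the treatment contrast can move either way.

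**Step 4: quality of life.** With 0.17 SD and loss unrelated to outcome, power is 77.5% at 5% loss (510 per arm) and 75.2% at 10% loss (483 per arm). Any cause of loss would have this effect.

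These calculations apply the loss to all 537 per arm and ignore deaths and ordinary loss to follow-up.

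**The case against.** A reader might infer that never-consented survivors get no 6-month visit. The documents do not say so. Sections 5.1 and 9.1 say all patients are seen, consent after tube placement is described as something to attempt, and data collection stops only on active withdrawal. A reader might also infer that nobody may consent after discharge. The limit in section 11.1.1.2 governs how long the coordinator searches. It does not bar later consent, and section 11.1.1.1 leaves consent open to the participant or to a representative identified later.

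Later contact routes exist too. Section 6.4 collects an emergency contact, alternate contacts and the discharge location, and restarts contact four to six weeks before month 6. A patient who has regained capacity can be reached and can consent. That narrows the affected group to survivors who still lack capacity and have no representative, and the documents do not size that group.

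Finally, a reader might infer that the loss must shrink the observed effect. Step 3 shows that this depends on who is lost.

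These points stand. What they leave is that the pre-visit contact in section 6.4 does not mention consent, that the open-ended wording of 11.1.1.1 comes with no continuing search, and that a statement that all patients will be seen does not tell staff how to proceed with an unconsented patient who lacks capacity.

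**Conclusion.** The narrower point holds, as a cheap improvement. The protocol ends active attempts to reach a representative at discharge, expects every patient at six months, and does not say how a survivor without capacity or a located representative is to be consented for that visit.

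The size is unknown. At the illustrative rates in Step 2, cognition power stays above the planned 80%, at about 83–84%, and the observed difference barely moves. It falls to or below 80% only under the heavier selective loss in Step 3. SF-36 power has no margin, since it is 79.5% with complete data. Understated prevalence rests on the plausible but undocumented assumption that the lost patients are more often impaired. No direction of bias in the treatment contrast can be claimed. The plan's stated power is not wrong; it assumes complete data.

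**What to change.** 1. In section 11.1.1.2, replace the hospital-discharge limit in both places with attempts to reach the participant or representative until the 6-month visit window closes, subject to IRB approval. Use the phone, mail and email routes in that section, and add consent to the pre-visit contact in section 6.4.
2. Reconcile sections 5.1, 9.1, 11.1.1.1 and 11.1.1.2, stating whether and how a survivor for whom consent has not been obtained may be approached and assessed at month 6.
3. Keep never-consented patients in the ITT population, as section 10.3 already defines it, and report their number by arm.
4. In section 10.2, add a not-missing-at-random sensitivity analysis for cognition, for example delta-adjusted imputation or a tipping-point analysis. A longer search cannot help a patient for whom no representative is ever found, so the analysis has to cover that remainder.

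The cost is a short IRB-approved protocol change, some added coordinator calls and letters through existing routes, and one further analysis. No new study procedure is needed.

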11.1.2 STUDY DISCONTINUATION AND CLOSURE

This study may be temporarily suspended or prematurely terminated if there is sufficient reasonable cause. Written notification, documenting the reason for study suspension or termination, will be provided by the suspending or terminating party to study participants, investigator, funding agency, the

Investigational Device Exemption (IDE) sponsor and regulatory authorities. If the study is prematurely terminated or suspended, the Principal Investigator (PI) will promptly inform study participants, the Institutional Review Board (IRB) and will provide the reason(s) for the termination or suspension. Study participants will be contacted, as applicable, and be informed of changes to study visit schedule.

Circumstances that may warrant termination or suspension include, but are not limited to:

- Determination of unexpected, significant, or unacceptable risk to participants
- Demonstration of efficacy that would warrant stopping
- Insufficient compliance to protocol requirements
- Data that are not sufficiently complete and/or evaluable
- Determination that the primary endpoint has been met
- Determination of futility

This study may be discontinued at any time by the DSMB's and or responsible IRB's recommendation. The study may resume once concerns about safety, protocol compliance, and data quality are addressed, and satisfy the funder, IRB and/or Food and Drug Administration (FDA).

